8.4.4 Other safety evaluations

8.4.4.1 First dose monitoring

For safety concern, the first dose of fingolimod administered at Day 1 in this study must be administered in the clinic under the supervision of the investigator. It is recommended that the first dose be administered in the morning, before 12 noon to allow for adequate monitoring time. The patient will stay at the study center for a minimum of 6 hours. Heart rate and blood pressure will be monitored hourly during the six hour stay and discharged if specific discharge criteria (outlined in [Section 16.5](#)) are met. Hourly monitoring will be extended if the discharge criteria are not met. Some participants may be required to return to the study center for 6 hours following the 2nd dose if they meet the monitoring criteria as outlined in [Section 16.5](#).

The investigator should promote compliance by instructing the patient to take the study drug exactly as prescribed and by stating that compliance is necessary for the participant's safety and

the validity of the study. The participant should be instructed to contact the investigator if he/she is unable for any reason to take the study drug as prescribed.

Should the participant interrupt the study drug, and should the investigator decide in agreement with the sponsor to re-initiate treatment with the study drug, the first dose intake at re-start must take place at the study site to ensure 6-hour monitoring by the First Dose Administrator in a similar manner as the first intake of the study drug. It is recommended not to initiate beta-blockers and calcium-channel blockers treatment in 24-hours prior or concomitant to re-initiation of the study drug administration due to a possible additive effect on heart rate reduction.

Monitoring of reinitiating of first dose will be performed when: interruption of 1 day or more within the first 2 weeks of treatment, interruption of more than 7 days during weeks 3 and 4 of treatment and interruption of more than 14 days after the first month of treatment.

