Prior to submission, the efficacy profile of fingolimod was evaluated in five main studies. In two of the phase III clinical trials, Study CFTY720D2301 (acronym FREEDOMS I) and CFTY720D2309 (acronym FREEDOMS II), each 24-month placebo-controlled study, fingolimod demonstrated reduction of relapse rate, disability progression, MRI lesion counts and rate of brain atrophy (Kappos et al 2010). In another Phase III trial, study CFTY720D2302 (acronym TRANSFORMS), a large active controlled study vs. intramuscular interferon beta-1a, fingolimod showed a significant reduction in relapse rate over the 12-month treatment period and reduced magnetic resonance imaging (MRI) lesion counts and rate of brain atrophy Kappos et al 2010. Study CFTY720D2399 (acronym LONGTERMS), an open-label, phase IIIb extension study, indicated that fingolimod treatment for up to 14 years had a sustained benefits for control of disease activity and disability progression without emerging safety concerns Cohen et al 2019. In the controlled pediatric study CFTY720D2311 (acronym PARADIGMS), it compared the efficacy of fingolimod to intramuscular interferon beta-1a in pediatric patients. It showed the annualized relapse rate (ARR), was significantly lower in patients treated with fingolimod than in patients who received interferon beta-1a.

The safety profile of fingolimod has been well characterized with approximately 296,714 patients in both clinical trials and the post –marketing setting, with the total patient exposure now at approximately 746,745 patient year by 30 Nov 2019. The safety profile in pediatric patients was overall similar to that seen in adult patients Chitnis et al 2018.

During the course of the fingolimod clinical development, several areas were identified as safety areas of note: bradyarrhythmias upon treatment initiation or on restarting after an interruption of fingolimod therapy of more than 14 days, liver transaminase elevations, hypertension, macular edema and infection.

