6.7.2 Instruction for prescribing and taking study treatment

- Fingolimod (Gilenya) 0.5 mg, 1 capsule, orally.
- Once daily, preferably always at the same time of the day, with or without food.
- The first dose of the study drug administered at the Day 1 visit, should be taken in the clinic preferably on or before 12:00 PM (noon). The participant will be monitored by the site staff for at least 6 hours until discharge criteria are met (refer to [Section 16.5](#) for Guidance for monitoring of patients taking their first dose of the study drug). Monitoring of re-initiation of first dose will be performed when: interruption of 1 day or more within the first 2 weeks of treatment, interruption of more than 7 days during the 3rd week and the 4th week of treatment and interruption of more than 14 days after the first month of treatment in a similar manner as the first intake of the study drug (refer to [Section 16.5](#) for Guidance for monitoring of patients taking their first dose of the study drug).
- The treatment will last up to 24 months.

- It is recommended not to initiate treatment with beta-blockers, calcium-channel blockers or digoxin within one week before or after the first dose of the study drug due to a possible additive effect on heart rate reduction.
- Site staff will make sure to dispense sufficient amount of study drug to participants. The amount should cover the period until participants come back to the clinic at the latest visit window allowed in the protocol. When the participants return for the following study visit, the site staff will count the capsules left, log the amount left into a drug accountability log and re-distribute the drug to the participants following the same procedure described above.
- It is a single-arm open label study. Participant eligible for the study will be treated with fingolimod (Gilenya).
- Participants should be instructed to swallow whole capsule and not to chew or open it.
- If vomiting occurs during the course of treatment, participants should not take fingolimod (Gilenya) again before the next scheduled dose.
- Participants should be instructed not to make up missed doses. A missed dose is defined as a case when the full dose is not taken within 8 hours after the approximate time of the usually daily dosing. That day's dose should be omitted and the participant should continue treatment with the next scheduled dose.

7 Informed consent procedures

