At Day1, two to three ECGs will be performed. The first ECG will be performed on Day 1 to check the I/E criteria again. If the participant is eligible to be enrolled, the ECG result will be recorded as pre-dose ECG. The second ECG will be performed approximately 6-hours post-first-dose. If extended monitoring is needed, then a third ECG will be performed by the end of extended monitoring.

If study drug treatment is interrupted and treatment re-initiation meets the requirement for observation, the above procedures will be repeated, identical to procedures conducted at Day 1.

For any ECGs with participant safety concerns, an additional ECG must be performed to confirm the safety finding. Clinically significant abnormalities must be recorded on the CRF as adverse events.

All the below ECG parameters will be captured in the eCRF: heart rate, PR interval, QRS duration, QT and QTc interval. Any diagnoses (or signs or symptoms if a diagnosis is not possible) associated with the abnormal findings should be recorded on the adverse event eCRF.

8.4.3 **Pregnancy and assessments of fertility**

To confirm an eligibility of a woman of child bearing potential for the study, a blood pregnancy test should be performed at Screening visit. Participants, who are determined and documented to be surgically-sterile or post-menopausal for 12 months or longer prior to Screening, are not required to undergo pregnancy testing.

Women of child-bearing potential, defined as all women physiologically capable of becoming pregnant, including women whose career, lifestyle, or sexual orientation precludes intercourse with a male partner and women whose partners have been sterilized by vasectomy or other means, unless they meet the following definition of post-menopausal: 12 months of natural

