8.4.4.2 Ophthalmic examination

A complete ophthalmic examination will be performed by an ophthalmologist as described in [Table 8-1](#).

At Screening and Month 3, Best Corrected Visual Acuity (BCVA) and Optical Coherence Tomography (OCT) for the measurement of central foveal thickness will be collected.

At all other scheduled visits, BCVA and new ophthalmic symptoms will be collected. In the case of confirmed visual acuity decline, an optical coherence tomography will be conducted by the investigator's discretion.

Details on the ophthalmic examinations are provided in the Guidance for Ophthalmic Monitoring [Section 16.6](#).

The ophthalmologist will describe examination findings on an examination worksheet provided by the investigative site. The worksheet will be transferred to the site where the data will be transcribed to the Ophthalmic Examination eCRF.

Participants with newly diagnosed uveitis after initiation of study drug will require more frequent ophthalmic evaluations. Refer to [Section 16.6](#) for the Guidance for Ophthalmic Monitoring for details on monitoring of participants with uveitis during the study.

During the study, participants with a diagnosis of macular edema must interrupt the study drug. These patients must be followed-up 1 month and 3 month after diagnosis of macular edema and more frequently if needed based on the ophthalmologist's judgement. Further ophthalmologic evaluations until such time as resolution is confirmed or no further improvement is expected by the ophthalmologist (based on a follow up period of not less than 3 months). If the participant does not show definite signs of improvement on examination by specialist testing (e.g. OCT, FA) 6-8 weeks after interruption of study drug, then therapy for macular edema in conjunction with an ophthalmologist experienced in the management of this condition should be initiated.

Re-initiation of the study drug can only be considered if the macular edema has resolved completely, the individual risk-benefit is favorable (as determined by the Investigator, in agreement with the Ophthalmologist) and after discussion with the Novartis Medical Advisor.

The patients must have follow up ophthalmic examinations at one month after study drug is re-initiated, three months later and then every 3 months up to one year, and every 6 months thereafter.

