- Heart rate at discharge must be at least 51 bpm (in patient 18 years or older), 55 bpm (in patients 12 years or older) or 60 bpm (in children \geq 10 years and below 12)
- Heart rate at discharge must be greater than 80% of baseline value ([Table 16-2](#) below)
- Heart rate at discharge must not be the lowest hourly value measured during the observation period (which would be suggestive of a continuing progressive decline in heart rate)
- Participants must have no symptoms associated with decreased heart rate
- ECG at 6 hours should not show any new significant abnormalities other than sinus bradycardia not observed at the patient's pre-dose ECG

Participants should have written instruction on when to return to clinic and a 24 hour contact phone number to call in the event of any new or warranted symptoms (chest pain, dizziness, palpitations, syncope, nausea and vomiting, etc.). Participants should be instructed not to drive themselves after the first dose of study drug administration.

Participants whose heart rate drops by more than 30% (as a result of strong sensitivity to the study drug) from pre-dose at any time during the 6-hour monitoring period may be discharged,

provided they meet the discharge criteria, but must return on Study Day 2 to take the second dose of the study drug and must be monitored as on Study Day 1.

If the above discharge criteria are not met, participants should continue to be observed until they are met. Participants experiencing any symptomatic event associated with reduction of the heart rate in the first 24 hours must take the Day 2 dose of study drug at the study center and must be monitored hourly for 6 hours before discharge. After the 6 hour monitoring participants may be discharged only if they meet the discharge criteria described above.

Table 16-2 Heart rate table for cardiac release criteria

Baseline Heart Rate	Minimum HR at 6hr post 1 st dose of the study drug eligible for release	HR reduction within 6hr monitoring indicating need for monitoring after 2 nd dose
45	40	31
46	40	32
47	40	33
48	40	33
49	40	34
50	40	35
51	40	35
52	41	36
53	42	37
54	43	38
55	44	39
56	45	39
57	45	40
58	46	41
59	47	41
60	48	43
61	49	43
62	50	43
63	50	44
64	51	45
65	52	46
66	53	46
67	54	47
68	54	48
69	55	48
70	56	49
71	57	50
72	58	50
73	58	51
74	59	52
75	60	53

Baseline Heart Rate	Minimum HR at 6hr post 1 st dose of the study drug eligible for release	HR reduction within 6hr monitoring indicating need for monitoring after 2 nd dose

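### Restart co-medication advice (two drug groups, 24 hours before or concomitant) is narrower than the Day 1 advice (three groups, one week either side), for the same heart-rate reason and without explanation

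*Protocol*

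**What the plan says.** For the first dose, Protocol 6.7.2 states: "It is recommended not to initiate treatment with beta-blockers, calcium-channel blockers or digoxin within one week before or after the first dose". For a restart, Protocol 8.4.4.1 recommends "not to initiate beta-blockers and calcium-channel blockers treatment in 24-hours prior or concomitant to re-initiation of the study drug". Each sentence ends with the same reason, a possible additive effect on heart rate.

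A restart that qualifies is otherwise handled much like a first dose. Section 6.7.2 sets the triggers: "Monitoring of re-initiation of first dose will be performed when: interruption of 1 day or more within the first 2 weeks of treatment", then more than 7 days in weeks 3 and 4, then more than 14 days after the first month. Section 8.4.4.1 adds that "the first dose intake at re-start must take place at the study site to ensure 6-hour monitoring by the First Dose Administrator". On ECGs, section 8.4.2 says that if dosing is interrupted and "treatment re-initiation meets the requirement for observation, the above procedures will be repeated, identical to procedures conducted at Day 1". Section 1.1 lists among the drug's notable safety areas "bradyarrhythmias upon treatment initiation or on restarting after an interruption of fingolimod therapy of more than 14 days".

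**The concern.** The stated hazard is the same at both doses, but the advice is weaker at a restart in three ways: a shorter period before dosing, no stated period after it, and no digoxin. No reason is given in 6.2.1, 6.2.2, 8.4.2, Appendix 5 (16.5), the amendment summaries or the SAP.

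What is at stake is participant safety in a narrow situation: a qualifying interruption, a restart, and a new rate-lowering drug started close to it. The days after the restart dose are the least protected. On-site observation ends at discharge on Day 1, or on Day 2 for those who meet the second-dose criteria, so it cannot cover a drug begun on a later day. New blood-pressure treatment is foreseeable, because Appendix 7 (16.7) refers participants with raised readings for treatment, possibly to a physician outside the study.

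**Working it through.** **Side by side**

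| | First dose (6.7.2) | Restart (8.4.4.1) |
|---|---|---|
| Drug groups | beta-blockers, calcium-channel blockers, digoxin (3) | beta-blockers, calcium-channel blockers (2) |
| Before dosing | one week | 24 hours |
| After dosing | one week | none stated beyond the undefined term concomitant |
| Reason | additive heart-rate effect | the same |
| Limit on interruption length | not applicable | none |

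The last row matters: the restart sentence covers every re-initiation, whether or not it meets the monitoring triggers.

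**Could residual drug explain the milder advice?** The half-life of 9 days is from SAP 2.1. First-order decay is an assumption. The fraction remaining after t days off drug is 2^(−t/9).

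- Shortest interruptions that trigger monitoring (6.7.2, 8.4.4.1): t = 1, 2^(−1/9) = 0.926; t = 8, 2^(−8/9) = 0.540; t = 15, 2^(−15/9) = 0.315.
- Macular edema follow-up points of 1 and 3 months (8.4.4.2; a month is 30 days in section 8): t = 30, 2^(−30/9) = 0.099; t = 90, 2^(−10) = 0.001.

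These are fractions of whatever had accumulated when dosing stopped, which in the first two weeks is below steady state. Nothing in the documents links residual drug to the heart-rate response at restart. The figures show only that a residual-drug rationale is plausible after a day or a week off drug and weak after a month or more.

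**Are long interruptions foreseeable?** Yes, for three reasons:

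- For macular edema, "Re-initiation of the study drug can only be considered if the macular edema has resolved completely".
- For transaminases reaching 5 times the upper limit on repeat, 16.7 requires interruption until values are normal, and reports normalisation within about 2 months of stopping.
- For confirmed lymphopenia, 16.7 expects recovery to take several weeks.

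**How many participants?** No rate is given for the full chain of interruption, restart and new drug, so none is estimated. Section 1.1 does give rates for two causes of a long interruption: macular edema 0.5% and transaminases at 5 times the limit or more 1.8%. In 100 participants that is 0.5 and 1.8 people, before requiring recovery, a restart and a new rate-lowering drug. Other causes of interruption have no rate in the documents.

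**The case against.** A reader might infer that the two sections conflict outright, so that an investigator cannot tell which rule governs. The protocol does sometimes attach the words first dose to a restart, as in the 6.7.2 trigger list and the 8.4.4.1 on-site rule. But both sections also tie the first dose of study drug to Day 1, restarts have their own sentence, and the specific text governs. Even if both rules applied, meeting the one-week rule would also meet the 24-hour rule before dosing. That stronger reading is not supported.

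A reader might also infer that the protocol's own parity rules make the narrower advice an error. They do not. Those rules cover monitoring and ECGs and set no co-medication window. Section 1.1 names restart bradyarrhythmia only after more than 14 days off drug, not after the one-day and eight-day interruptions that also trigger monitoring. A shorter window after a short interruption may be intended.

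Existing safeguards also count. Restart needs sponsor agreement. There is hourly observation for 6 hours, with ECGs before dosing and at 6 hours. Appendix 5 (16.5) says the initiation effect is maximal within 6 hours, inside the observed period, and warns about drug-induced low heart rate before dosing. It sets discharge criteria, gives participants return instructions and a 24-hour contact number, and those whose heart rate falls by more than 30% "must return on Study Day 2 to take the second dose of the study drug and must be monitored as on Study Day 1". Participants are told to report new medication (6.2.1).

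What remains is an unexplained difference for the same stated reason, least defensible after long interruptions. Appendix 5 also says the initiation effect wears off over days to weeks, so some of it may outlast discharge.

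**Conclusion.** The point holds as a minor wording matter. The restart advice is narrower than the Day 1 advice in window and drug list, and no reason is given. This matters chiefly for monitored restarts after long interruptions. The documents do not show that the narrower advice is wrong for short ones.

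The textual difference is certain. Its clinical weight is a matter of judgement, resting on the assumption that a restart with little drug left behaves much like a first dose. Section 1.1 supports that for interruptions of more than 14 days, and the decay figures are only indicative. Few participants are likely to be affected. The annualized relapse rate analysis, the sample size and the SAP are unaffected.

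**What to change.** In Protocol 8.4.4.1, keep the 24-hour advice for every re-initiation, so that restarts below the monitoring triggers do not lose it, and add digoxin to its drug list. Then add a sentence to this effect: *For a re-initiation that requires first-dose monitoring, we recommend that no beta-blocker, calcium-channel blocker or digoxin be newly started during the week before or the week after the restart dose.*

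If a shorter window after short interruptions is intended, the sponsor may limit the one-week advice to interruptions of more than 14 days, which matches section 1.1.

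The cost is a small change of protocol wording. No new data are needed, because concomitant medication is already recorded (6.2.1 and Table 8-1). The downside is that a restart, or a new rate-lowering drug, may be delayed by up to a week. The text stays a recommendation, so the investigator can depart from it when treatment is urgent.

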8.4.4.2 Ophthalmic examination

A complete ophthalmic examination will be performed by an ophthalmologist as described in [Table 8-1](#).

At Screening and Month 3, Best Corrected Visual Acuity (BCVA) and Optical Coherence Tomography (OCT) for the measurement of central foveal thickness will be collected.

At all other scheduled visits, BCVA and new ophthalmic symptoms will be collected. In the case of confirmed visual acuity decline, an optical coherence tomography will be conducted by the investigator's discretion.

Details on the ophthalmic examinations are provided in the Guidance for Ophthalmic Monitoring [Section 16.6](#).

The ophthalmologist will describe examination findings on an examination worksheet provided by the investigative site. The worksheet will be transferred to the site where the data will be transcribed to the Ophthalmic Examination eCRF.

Participants with newly diagnosed uveitis after initiation of study drug will require more frequent ophthalmic evaluations. Refer to [Section 16.6](#) for the Guidance for Ophthalmic Monitoring for details on monitoring of participants with uveitis during the study.

During the study, participants with a diagnosis of macular edema must interrupt the study drug. These patients must be followed-up 1 month and 3 month after diagnosis of macular edema and more frequently if needed based on the ophthalmologist's judgement. Further ophthalmologic evaluations until such time as resolution is confirmed or no further improvement is expected by the ophthalmologist (based on a follow up period of not less than 3 months). If the participant does not show definite signs of improvement on examination by specialist testing (e.g. OCT, FA) 6-8 weeks after interruption of study drug, then therapy for macular edema in conjunction with an ophthalmologist experienced in the management of this condition should be initiated.

Re-initiation of the study drug can only be considered if the macular edema has resolved completely, the individual risk-benefit is favorable (as determined by the Investigator, in agreement with the Ophthalmologist) and after discussion with the Novartis Medical Advisor.

The patients must have follow up ophthalmic examinations at one month after study drug is re-initiated, three months later and then every 3 months up to one year, and every 6 months thereafter.

8.4.4.3 Pulmonary function test

Pulmonary Function tests evaluating forced expiratory volume within 1 second (FEV1) and carbon monoxide (CO) diffusing capacity (DLCO) will be performed for all the patients at screening period and can be performed when participants with any reported AE related to respiratory disease during the treatment period, as per investigator discretion.

The FEV1 describes the volume (in Liters) that is expelled within one second of forced expiration after a maximal inspiration and reflects the large airway resistance. A decrease in FEV1 serves as a good parameter for detection of an obstructive ventilatory defect.

Gas exchange is assessed by the DLCO evaluated by the single breath holding method. It is a measurement of carbon monoxide (CO) transfer from the lung over a breath-holding period to pulmonary capillary blood. Because the CO binds readily to hemoglobin, the diffusion capacity needs to be corrected for hemoglobin in order to reflect an altered lung gas transport rather than altered hemoglobin.

Based on the investigator's judgement, pulmonary function test (PFT) can be performed when participants with AE related to respiratory disease during the treatment period. In case of reduction of FEV1 and/or DLCO below 80% of baseline values the patient's pulmonary status will require a follow-up as soon as possible. Should the repeat PFT values (FEV1 and/or DLCO) remain below 80% of baseline values, the patient will be referred to pneumologist (pulmonologist) for further evaluation and treatment. In case of reduction of FEV1 and/or DLCO below 60% of baseline value in any visit, the study drug is recommended to be interrupted and suggest to refer the patient a pneumologist (pulmonologist) immediately for further evaluation and treatment. In case of persistent reduction of FEV1, and/or DLCO below 80% of baseline values over 3-month period despite of appropriate treatment, the Primary Treating Physician may consider an interruption of the study drug. This decision may be discussed with Novartis Medical Advisor. Investigators will be asked to comment on the result of pulmonary function test. The pulmonary function test report will be filed with the source documents. Abnormal results and any diagnoses (or signs or symptoms if a diagnosis is not possible) associated with the abnormal findings should be recorded on the adverse event eCRF.

